#### 8.9.6 Stopping Rule

Enrollment into the study will be temporarily halted if the Sponsor receives a SAE for a vascular embolic event that lead to skin necrosis, vison loss, or stroke and is determined by the Investigator to be directly or possibly related to the study device or injection procedure. The SAE will be investigated by the Sponsor. If the Sponsor's investigation concludes:

- The SAE was unanticipated, directly related to the study product or device injection procedure, and presents an unreasonable risk to study subjects, the study will be terminated and the Investigators notified. The IRB and RA will also be notified if the study is prematurely terminated due to safety concerns.
- If the SAE does not meet the above criteria, then enrollment in the study will continue.

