#### 5.4 Screening and subject numbers

Prior to any study procedures being conducted, the subject must sign the informed consent form. The subject number will be assigned at the screening visit. All study procedures performed should be documented in the subject's source documents and in the electronic Case Report Forms (eCRFs). The subject number, subject name and other information sufficient to link the eCRF to the medical records (e.g. national identification number, chart number, etc.) should be recorded.

A screen failure is a subject who signed informed consent but never enrolled (i.e. received treatment) in the study. For screen failures, the subject's source documents should indicate which assessments have been made and the reason why the subject was determined to be a screen failure.

2021-02-09 21:57

A subject is considered enrolled when they have signed the ICF and are randomized and/or treated.

During the study conduct, the Blinded Evaluators should not have access to any subject's source documents that identify the subject.

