#### 8.9.5 Reporting of serious adverse events

The Investigator should report any SAE to the Sponsor immediately but not later than 24 hours of awareness of the event. This initial report can be made via e-mail.

In case of difficulty to obtain all the required information within 24 hours, an initial report can be submitted, with the following information as a minimum, irrespective of whether some of it is regarded as preliminary:

- CTN: 43USCH1702
- Subject identification (age, gender, subject number)
- Adverse event description
- Date when AE occurred
- Date when AE became serious
- Name of Investigator and original reporter (if other than the Investigator)
- Name of device: Restylane® Defyne (investigational)
- Treatment specification

Follow-up information and data missing in the initial SAE reporting should be gathered as soon as possible and reported immediately but not later than 24 hours of awareness of the new data. Complete and adequate information on each SAE is required. All attempts to obtain this information, including dates for follow-up activities, must be documented by the Investigator or designated study staff.

Doc id 43USCH1702 Protocol ♣ GALDERMA

Print date:

2021-02-09 21:57

Supporting documentation to be provided with the SAE report:

- Concomitant medication form
- Concomitant procedure/treatment form
- Study treatment CRF form
- AE form
- Medical history form
- Any other relevant supporting documentation (e.g. hospital notes, death certificate, autopsy reports etc.)

The SAE form must be signed and dated by the Investigator. If the initial 24-hour SAE report does not contain full information or if it is made without using the SAE form the fully completed and signed SAE form should be e-mailed to the Sponsor. A copy of the fully completed SAE form should be kept at the site.

In addition, the Investigator should report SAEs to the responsible IRB without undue delay, if applicable according to national regulations. The Investigator is responsible for checking what reporting procedures are applicable for his/her IRB regarding SAEs and final report of the outcome of the study and to comply with such reporting procedures during the study period. For non-urgent complementary information not possible to send by e-mail or fax, please use surface mail.

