# 15. Suspension or Premature Termination

The Sponsor will suspend or terminate the study when so instructed by the IRB or FDA, or if it is judged that the subjects are subjected to unreasonable risks, or for valid scientific or administrative reasons.

The Sponsor may also decide to close a single study site due to unsatisfactory subject enrollment or non-compliance with the CIP, GCP, or applicable regulatory requirements.

In the event of premature termination, the Sponsor will provide information on the handling of currently enrolled subjects who have not completed the study.

Title
43USCH1702 Protocol

Doc id

2021-02-09 21:57

Print date:

Page 69 of 72

Title
43USCH1702 Protocol Doc id 🚣 GALDERMA

[figure not shown]
Print date:

2021-02-09 21:57

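### The stopping rule for vascular embolic events pauses enrollment but not further injections in subjects already enrolled

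*Protocol*

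**What the plan says.** The rule in Protocol 8.9.6 begins: "Enrollment into the study will be temporarily halted if the Sponsor receives a SAE for a vascular embolic event". The event must have led to skin necrosis, loss of vision or stroke, and the Investigator must consider it at least possibly related to the device or the injection. The Sponsor then investigates, with no time limit given.

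There are two outcomes. If the event was unanticipated, directly related and "presents an unreasonable risk to study subjects, the study will be terminated and the Investigators notified". Otherwise: "If the SAE does not meet the above criteria, then enrollment in the study will continue".

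Other parts of the protocol also bear on this:

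- Section 8.9.5 on reporting: "The Investigator should report any SAE to the Sponsor immediately but not later than 24 hours of awareness of the event".
- Section 15 on suspension: the Sponsor suspends or ends the study on an instruction from the IRB or the FDA. The remaining grounds are: "or if it is judged that the subjects are subjected to unreasonable risks, or for valid scientific or administrative reasons".
- Section 5.5 lets the Investigator discontinue an individual subject.

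The protocol's definitions list describes touch-up as a further injection after treatment. SAP 12.0 lists four kinds of injection: initial treatment, optional touch-up and optional re-treatment in the treatment arm, and an optional first treatment in the control arm. SAP 13.1 groups adverse events in a way that confirms the last two.

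**The concern.** The rule is triggered by harm attributed to an injection, but its only automatic response is to stop bringing in new subjects. A subject already in the study who is due a touch-up, a re-treatment or, as a control, a first treatment would receive the same product by the same route. Section 8.9.6 neither delays that injection nor mentions it.

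The period at issue runs from the SAE report to the end of the Sponsor's investigation. In that period the causal question is still open, and 8.9.6 leaves injections running unless the Sponsor, the IRB, the FDA or an Investigator separately decides otherwise. The outcomes guarded against can be permanent, while at least three of the four kinds of injection are optional and could wait.

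**Working it through.** No arithmetic beyond a count applies. The check sets the scope of the pause against the injections that remain.

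**1. What is paused.** Section 8.9.6 reads as continuous text. It names enrollment as the thing halted and, in the closing bullet, as the thing resumed. Injections appear in neither place.

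**2. Who is already enrolled.** Protocol 5.4 gives two meanings.

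- Definition A, in the screen-failure sentence, equates enrollment with treatment: "A screen failure is a subject who signed informed consent but never enrolled (i.e. received treatment) in the study".
- Definition B is the explicit one: "A subject is considered enrolled when they have signed the ICF and are randomized and/or treated".

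**3. Which injections the pause reaches.** The four categories are those in SAP 12.0.

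| Injection | A: enrolled when treated | B: enrolled when randomized and/or treated |
|---|---|---|
| Initial treatment (treatment arm) | Paused | Paused, except for a subject already randomized but not yet injected |
| Optional touch-up (treatment arm) | Not paused | Not paused |
| Optional first treatment (control arm) | Paused | Not paused |
| Optional re-treatment (treatment arm) | Not paused | Not paused |
| Categories wholly outside the pause | 2 of 4 | 3 of 4 |

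Touch-up and re-treatment are outside under both definitions. The controls' first treatment depends on which sentence of 5.4 a site applies.

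**4. After accrual closes.** No enrollment is left to halt, so the automatic pause has no effect. The duty to investigate, and termination if the criteria are met, remain. Protocol 4.3 gives about 17.5 months from screening to final visit, so most of the last subject's participation falls after accrual. When re-treatment is given cannot be read.

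**5. Whether another provision imposes the pause.**

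- The 24-hour report (8.9.5) informs the Sponsor but stops nothing.
- Termination (8.9.6) follows the investigation and so cannot cover the time it takes.
- Suspension (section 15) needs an instruction, a judgement of unreasonable risk, or a decision that some other valid reason applies.
- Individual discontinuation (5.5) is subject by subject and depends on the Investigator knowing of the event. Section 8.9.6 provides for notifying Investigators only on termination. An enrollment halt would alert sites in practice, but after accrual there is no such signal.

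None of these automatically pauses injections between the report and the conclusion.

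**The case against.** The strongest reply is section 15. Its last limb lets the Sponsor suspend the study for valid scientific or administrative reasons, with no prior finding of unreasonable risk. A Sponsor investigating a possibly related stroke could use it the same day, and injections would stop. The pause in 8.9.6 also rests on a judgement, since the Investigator must first assess relatedness. On this view the only gap is that the pause on injections is not committed in advance. That is a fair description of the point, and it does not remove it: once relatedness is judged possible, the enrollment halt is mandatory, whereas every limb of section 15 needs a further decision or instruction.

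Three other objections limit the reach of the point:

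- **Redaction.** Much of the design, schedule, exclusion and treatment text is blacked out, and the study-specific instructions for use are not available. A condition for withholding injections could sit there. This cannot be excluded, although 8.9.6 refers to none.
- **Versions.** The rule is from protocol version 5.0. The controls' first treatment and re-treatment are known only from a SAP based on version 3.0 (SAP 1.0). Touch-up does not depend on the SAP, because version 5.0 defines it.
- **Size.** Counting categories measures scope, not risk. It says nothing about how many injections would fall due during a halt.

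A blanket hold also has a price. SAP 3.1.1 times the primary assessment at 12 weeks after the last injection in the treatment arm, so a delayed initial treatment or touch-up moves that visit.

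**Conclusion.** The point holds as a statement about what 8.9.6 itself does. After a qualifying event it automatically pauses enrollment only, and it does not pause later injections in enrolled subjects while the Sponsor investigates. Its action does not match its injection-related trigger.

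By category, 2 of 4 kinds of injection lie outside the pause under either definition of enrolled, and 3 of 4 under the explicit one. This rests on the SAP categories still applying under protocol version 5.0; for touch-up no such assumption is needed. The number of injections affected depends on uptake, on when a halt falls and on how long it lasts, none of which the documents give.

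Discretionary protections exist, so subjects are not left without safeguards. This is a change the sponsor should make, and it does not mean that injections could not be stopped under the present protocol.

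**What to change.** Amend 8.9.6 so that a qualifying event temporarily halts *enrollment and all study injections* until the Sponsor's investigation concludes, and state that this applies after enrollment has closed. Follow-up and safety visits should continue during the halt. Change the closing bullet so that *enrollment and study injections* resume together. Naming injections directly also removes any dependence on the two meanings of enrolled in 5.4. If a withholding condition already exists in the treatment sections, a cross-reference to it in 8.9.6 is enough.

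The cost is a short amendment and a notice to sites. Beyond that, a cost arises only if the rule is triggered: some injections, and visits timed from them, may then fall outside their windows, including the 12-week primary assessment after a delayed initial treatment or touch-up. This cannot be sized because the visit windows are not readable.

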# 8.9.7 Follow-up of ongoing related events after termination of the study and events with onset after termination of study (subject last visit)

All serious as well as non-serious AEs with a causal relationship to the study product or treatment procedure and ongoing at study end, should be followed up after the subject's participation in the study is over. Such events should be followed-up after the last study visit until resolved, or assessed as chronic or stable. All AEs assessed as related to the

2021-02-09 21:57

study product or treatment procedure, serious as well as non-serious, with onset after the study termination (last subject study visit), and that the Investigator becomes aware of, should be reported to the Sponsor by email to

#### 8.9.8 Pregnancy

Pregnancy itself is not regarded as an AE.

If there is a pregnancy after the subject has been treated, the subject must continue to be followed and the outcome of pregnancy must be reported even if the delivery occurs after study completion.

A pregnancy confirmed during the study period after treatment must be reported by the Investigator on a pregnancy report form immediately upon acknowledgement and submitted to the Sponsor according to contact details specified in Section 8.9.5. The report can be prospective or retrospective. Follow-up should be conducted to obtain outcome information on all prospective reports.

Cases that led to fetal distress, fetal death or a congenital abnormality or birth defect are to be regarded as SAEs and should be reported on the exposure in utero report form to the Sponsor immediately but no later than 24 hours after the Investigators awareness. These events should be handled as SAEs during data processing. Other complications during the pregnancy that are related to the pregnant woman and fulfils any serious criteria, such as pre-eclampsia requiring hospitalization, should be reported and handled as SAEs. Elective abortions without complications should not be reported as AEs.

#### 8.9.9 Anticipated adverse events

Information regarding anticipated AEs for Restylane® Defyne (investigational) is included in the study specific IFU.

#### 8.10 Device deficiencies

#### 8.10.1 Definition of a device deficiency

A device deficiency is defined as an inadequacy of a medical device with respect to its identity, quality, durability, reliability, safety, or performance.

Note: Device deficiencies include malfunctions, use errors, and inadequate labelling.

#### 8.10.2 Recording instructions

When a device deficiency is discovered, Part A of the clinical study complaint form should be completed by the Investigator or qualified designee. The type of complaint should be described and injury to the subject or user or unintended exposure to study product should be reported as applicable. If an injury has occurred, an AE or an SAE form should be completed as applicable (refer to Section 8.9.4 and 8.9.5). If no SAE was experienced as a result of the device deficiency the Investigator should assess whether or not the device deficiency could have led to an SAE if:

- Suitable action had not been taken,
- Intervention had not been made or,

<sup>1Inadequacy of device safety refers to properties of the device which could have or have led to an AE.

• Circumstances had been less fortunate

In Part B of the clinical study complaint form the Sponsor will make the same assessment.

#### 8.10.3 Reporting of device deficiencies

The Investigator should send the completed clinical study complaint form to the Sponsor by email to

A device deficiency that led to a SAE and any device deficiency that is assessed as it could have led to a SAE should be reported within 24 hours after the Investigator's awareness in accordance to Section 8.9.5.

In order to fulfil regulatory reporting requirements, all deficiencies with the study product must be assessed by both the Investigator and the Sponsor to determine if it could have led to a SAE.

If a SAE has resulted from a device deficiency or if either the Investigator or the Sponsor assesses that the device deficiency could have led to a SAE the Sponsor is responsible for reporting the device deficiency to RA and the PI is responsible for reporting it to the IRB.

The deficient study product should be kept by the study site until the Sponsor has confirmed whether the product should be returned to Sponsor for further study or if it can be destroyed at the study site.

## 9. Data Handling and Management

#### 9.1 Data management

Data management based on GCP refers to the activities defined to achieve safe routines to enter clinical data information into a database, efficiently and avoiding errors. The data management routine includes procedures for handling eCRFs, database set-up and management, data entry and verification, data validation, and documentation of the performed activities including information of discrepancies in the process. The data management process will be described in detail in the data management plan (DMP).

The database, the data entry screens and program will be designed in accordance with the CIP and the eCRF. Data validation will be performed by computerized logical checks and manual review. Drugs and events will be coded in accordance with World Health Organization (WHO) Drug and medical dictionary for regulatory activities (MedDRA) dictionaries as specified in the DMP. SAEs in the clinical database will be reconciled against the data in the safety database.

When all efforts have been made to ensure that the data recorded in the eCRFs and entered in the database is as correct and complete as possible, the clinical database will be locked. Study data will be transferred to SAS datasets which thereafter will be write-protected. Statistical analyses will be generated in SAS using data from the locked datasets.

#### 9.2 Electronic case report forms

A 21 Code of Federal Regulations Part 11-compliant electronic data capture application will be used to collect, modify, maintain, archive, retrieve, and transmit study data. An eCRF is required and should be completed electronically for each screen failure as well as enrolled subjects.

The eCRF includes password protection and internal quality checks, such as automatic range checks, to identify data that appear inconsistent, incomplete, or inaccurate. Study data should

2021-02-09 21:57

be entered directly from the source documents, which are to be defined at each site before inclusion of the first subject.

Authorized study site personnel designated by the Investigator should complete data collection. Appropriate training and security measures should be completed with all authorized investigation site personnel prior to the study being initiated and any data being entered into the system for any subject.

The study data is the sole property of the Sponsor and should not be made available in any form to third parties, except for authorized representatives of appropriate RA, without written permission from the Sponsor. At the end of the study, electronic data are kept at the Sponsor and a copy (provided by the vendor) at the study site as part of the Investigator file.

Any delegation of collection of data should be specified in a signature and delegation log.

#### 9.2.1 Data entry

All data should be entered in English. The eCRFs should always reflect the latest observations on the subjects participating in the study. Therefore, the eCRFs should be completed as soon as possible during or after the subject's visit. The subject's identity must always remain confidential, i.e. the name and address of the subjects must not be registered in the eCRFs or in the database. The Investigator must verify that all data entries in the eCRFs are accurate and correct. If some assessments are not done, or if certain information is not available, not applicable or unknown, the Investigator should indicate this in the eCRF. The Investigator should electronically sign off the study data. By signing, the Investigator takes responsibility for the accuracy, completeness, and legibility of the data reported to the Sponsor in the eCRF.

#### 9.2.2 The query process

The monitor should review the eCRFs and evaluate them for completeness and consistency. Each eCRF should be compared with the respective source documents to ensure that there are no discrepancies between critical data. All entries, corrections, and alterations should be made by the PI or his/her authorized designee. The monitor cannot enter data in the eCRFs. Once study data have been submitted to the central server via the eCRF, corrections to the data fields will be audit trailed, meaning that the reason for change, the name of the person who made the change, together with time and date will be logged. Roles and rights of the site personnel responsible for entering study data into the eCRF should be determined in advance. If discrepant data is detected during review of the data, either by the Sponsor or its representatives, the responsible data manager or monitor should raise a query in the electronic data capture application. The query should state the question or data to be changed and should be resolved in the system by the PI or his/her authorized designee. The appropriate study site personnel should answer the queries in the eCRF. This will be audit trailed by the electronic data capture application meaning that the name of study site personnel, time, and date is logged.

### 9.2.3 User identification

eCRF records will be automatically appended with the identification of the creator, by means of their unique User ID. Specified records should be electronically signed by the Investigator to document his/her review of the data and acknowledgement that the data are accurate. This will be facilitated by means of the Investigator's unique User ID and password; date and time stamps will be added automatically at time of electronic signature.

2021-02-09 21:57

If an entry in an eCRF requires change, the correction should be made in accordance with the relevant software procedures.

#### 9.2.4 Audit trail

All changes will be fully recorded in a protected audit trail and a reason for the change should be stated. Once all data have been entered, verified, and validated, the database will be locked.

#### 9.3 Source documents

Source documents are all documents used by the Investigator or hospital that relate to the subject's medical history, that verifies the existence of the subject, the inclusion and exclusion criteria, and all records covering the subject's participation in the study. They include laboratory notes, memoranda, material dispensing records, subject files, etc.

The Investigator is responsible for maintaining source documents. These should be made available for inspection by the monitor at each monitoring visit. The Investigator must submit a completed eCRF for each subject for whom signed informed consent has been collected. All supportive documentation submitted with the eCRF, such as laboratory or hospital records, should be clearly identified with the CTN and subject number. Any personal information, including name, should be removed or rendered illegible to preserve individual confidentiality.

